## 2 RATIONALE

Nowadays, prematurity is a central issue both for obstetrics as well as for public health worldwide, as it is a highly incident clinical situation (affecting approximately 7% to 10% of births), and is involved in around 50 - 75% of neonatal morbidities and mortalities, mainly in neonates born before 32 weeks of gestation. Sequelae in premature neonates also impact on the increase of healthcare costs and infant mortality during the first year of life (1).

The rate of preterm births has not declined over the last 20 years, and in most developed countries it remains high despite advances in the knowledge about risk factors and mechanisms related to preterm births (2). Essentially, there are two reasons that explain the failure to reduce preterm births: first, the absence of a screening method effective for the identification of women at high risk for this event; and second, the lack of effective intervention to prevent this complication.

The most commonly adopted approach for identification of pregnancies at high risk for preterm birth has been the use of obstetrical history and mother's demographics.

In published screening studies where over 60,000 women with single pregnancies were included, the preterm birth rate by week 34 in England was 1.8%, very similar to that found in our country (1.3%). Preterm births were spontaneous in two-thirds of the cases (1.2% of the total), whereas one-third were iatrogenic. Only in 3% of cases, the patients had a history of preterm birth and this group accounted for 15% of the total number of spontaneous deliveries by week 34 only. This demonstrates that identification of patients at risk of delivery before week 34 based on obstetric history leaves most of these patients outside of the risk group, and therefore, not covered by preventive measures.

An effective method for prenatal screening to detect the risk of preterm birth is the measurement of the cervical length by ultrasound between gestation weeks 20 and 25. The risk of preterm birth both for single-fetus as well as for twin pregnancies is inversely related to the cervical length. Therefore, a woman with a cervical length (CL) between 1-10 mm has a risk of preterm birth of 44%, whereas a woman with a CL between 26-30 mm has a risk of 1.3%. The group with cervix measures of 1 to 15 mm corresponded to 28% of all spontaneous deliveries before week 34, and the group with a cervix measure of 16 to 25 mm corresponded to 21% (3).

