5.4.3. After insertion of the pessary or beginning of the administration with vaginal progesterone capsules and until 28 weeks of gestation, participants in the 3 treatment groups will be monitored every 4 weeks at the most or more often, if the site has established so as a control standard. After 28 weeks, patients should be monitored every 2 weeks. At every control visit, procedures applicable to their prenatal control and a transvaginal ultrasound by standard technique will be performed (patients receiving vaginal capsules), if considered necessary by the physician, or transvaginal using the technique recently described (25) (in patients with medicated pessary) to measure and record cervical length. The occurrence of possible side effects, adherence to treatment, and visits or hospitalizations due to threat or preterm labor will also be recorded, as well as the existence of potential causes for *ex-post* exclusion from the study. In addition, concomitant medication will be recorded at each visit.

5.4.4 Management of participants consulting due to a threat or premature labor will be conducted according to the diagnostic and therapeutic guidelines of the Ministry of Health (MINSAL) (Clinical Guide for Preventing Preterm Birth - MINSAL 2010) and the respective hospital's Obstetrics and Gynecology Service. In these cases, the treating physician will be provided with information about the progesterone treatment the patient is receiving in the study, and the decision for her continuation in the clinical study will be made jointly as far as possible, since the opinion of the treating physician shall predominate.

5.4.5 Every case will be closed at 36 6/7 weeks of gestation, or at the time of preterm birth. Data on the birth, condition at birth, and evolution of infants born preterm will be analyzed, recording morbidity and mortality through the time of discharge from the hospital.

The participant's attending health team (physicians and midwives) will be informed in writing about the participation of these women in the study by means of an identification

card that will be given to every woman participating in the study. In the pregnancy card, participation of these subjects in the study will be emphasized by means of a self-adhesive sticker detailing their participation in one of the treatment groups (pessary or capsule) and recorded in the medical history.

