#### 5.5. Placement and repositioning of the cerclage pessary containing sustained-release progesterone

Once the cervix length and positioning have been examined by transvaginal ultrasound, and any vaginal infection has been ruled out or treated, the progesterone pessary should be implanted by a professional qualified and trained for that purpose. For placement, the participant must be lying in supine position.

The removal of the pessary will be done by vaginal examination at week 36 6/7 or earlier, if there is any medical indication for induction of premature labor or elective cesarean section. The pessary will also be removed from participants in preterm birth labor not responding to treatment with tocolytics.

During controls or visits to emergency departments or medical offices, participants who report vaginal discharge should be examined by a physician to rule out infection by relevant testing (vaginal discharge smears for PCR), and deliver the appropriate treatment without the need to remove the pessary. This condition will be considered an adverse event.

In the event that the medicated cerclage pessary is spontaneously expelled it, will be repositioned within maximum 72 hours; if this does not occur, the patient will be withdrawn from the study but considered in the final statistical analysis under the intention-to-treat principle.

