#### **Definition of Adverse Event of Special Interest**

Adverse events of special interest are adverse events considered important for assessment of the safety profile regardless of seriousness, expectancy, and severity classification.

Preterm birth is the birth of a fetus before 37 weeks of pregnancy. Preterm birth will be considered an event of special interest and should consequently be reported within 24 hours.

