## **9 STATISTICS**

This project aims to conduct a randomized, open-label, controlled, clinical-exploratory phase II study evaluating the efficacy of a cerclage pessary containing one of 2 doses of sustained-release micronized progesterone for prevention of preterm birth, compared to the treatment method currently used by obstetrics-gynecology specialists, which comprises the administration of one daily capsule by vaginal route of 200 mg of progesterone. A total of

270 pregnant participants at risk of preterm birth will be enrolled, screened, and randomized to the 3 groups of treatment previously described. The number of patients listed ( $n = 270$ ) refers to the number of patients who effectively are enrolled and successfully complete the study. Therefore, an enrollment of at least 10% over that number (27 patients or more) should be considered due to the eventual withdrawal or early loss to follow-up of patients initially recruited.

As primary results, the proportions of spontaneous preterm delivery before gestation weeks 32 and 34 will be compared between the control group and the 2 groups with the pessaries containing different doses of progesterone. The risk of spontaneous preterm birth from the time of inclusion in the study through the gestation weeks 32 and 34 will be determined by a Kaplan-Meier analysis, where gestational age will be the time scale and spontaneous delivery will be the event; elective parturitions will be censored. For the purpose of this analysis, pregnancies will no longer be considered as high risk for the event if delivery occurs at the week of gestation 34 (34 0/7) or beyond.

As secondary outcomes, those qualitative variables in pregnant participants at risk of preterm birth will be evaluated, and the percentage distribution of acceptability responses or side effects recorded will be determined. For the quantitative variables (measurements of length and cervical angulation), the averages and standard deviations of the values found will be compared. Accordingly, each participant will work as her own control.

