this is in terms of decrease of the proportion of pregnancies with premature risk. In this way it will be determined the effective response to progesterone in the cerclage pessary through the occurrence of spontaneous delivery after 32 weeks but before 34 weeks of gestation. The evaluation of the error type 1 will be with a value of 0.05 for the type of variable being used.

As part of the exploratory analysis for the efficacy of treatments, the risk of spontaneous premature birth from the moment of inclusion in the study until the weeks 32 and 34 of gestation, will be determined with the Kaplan-Meier analysis, where the gestational age is the timeline, spontaneous delivery will be the event and elective deliveries will be censored. A singleton pregnant subject between 16 and 24 weeks of gestation will be eligible to participate in the study when she meets one of the following two conditions:

- Cervical length between 10 to 25 mm and without risk factors
- Cervical length greater or equal to 10 mm and with pre-existing risk factors in the immediate preceding pregnancy characterized by:
 - premature delivery before the week 35 (with a viable fetus)
 - premature rupture of membrane prior to week 35 (with a viable fetus)

There are two ways to measure the gestational age which are the following:

- Gestational Age according to DLNM (weeks)
- Gestational Age according to Transvaginal Ultrasound (weeks)

The time of gestational age will be evaluated through log-rank tests among treatments. The null hypothesis is stated as the no treatment differences in the gestational ages.

Kaplan-Meier (product limit) estimates of the gestational age distribution will be calculated and their corresponding 95% confidence interval (CI) will be presented: 25th percentile, mean, median, and 75th percentile.

The analysis will be performed for the two measurements of gestational time, considering the Transvaginal ultrasound the one most accurate.

For the purposes of this analysis, pregnancies will no longer be considered of high risk in the event birth takes place in week 34 (34 0/7) of gestation or more.

SECONDARY ANALYSIS

For some of the secondary variables, subjects will be their own controls in the following variables to evaluate and the following analysis are proposed:

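### Spontaneous births at 34 0/7 to 36 6/7 are not clearly counted in any efficacy comparison, although pessary use and planned follow-up run to 36 6/7

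*Protocol*

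**What the plan says.** **Treatment and follow-up.** Protocol 5.5: "The removal of the pessary will be done by vaginal examination at week 36 6/7 or earlier". Protocol 5.4.5: "Every case will be closed at 36 6/7 weeks of gestation, or at the time of preterm birth".

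**Definition.** The only definition of preterm birth is in Protocol section 8, under adverse events of special interest: "Preterm birth is the birth of a fetus before 37 weeks of pregnancy". These births must be reported within 24 hours.

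**Efficacy comparisons.** Under Protocol section 9, "the proportions of spontaneous preterm delivery before gestation weeks 32 and 34 will be compared between the control group" and the two pessary groups. The Kaplan-Meier analysis covers "The risk of spontaneous preterm birth from the time of inclusion in the study through the gestation weeks 32 and 34", with spontaneous delivery as the event and elective deliveries censored. The limiting rule follows: "pregnancies will no longer be considered as high risk for the event if delivery occurs at the week of gestation 34" (34 0/7) or beyond. SAP section 10 repeats it: "pregnancies will no longer be considered of high risk in the event birth takes place in week 34". Membrane rupture, the other pregnancy outcome compared between arms, also stops at 34 weeks (Protocol 7.2.1, SAP 10).

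**Other SAP outputs.** SAP section 10 labels the Kaplan-Meier work exploratory. It adds log-rank tests of gestational age among treatments, with the 25th percentile, mean, median and 75th percentile. Those sentences give no upper limit on gestational age.

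**Classification of births.** Protocol 5.8 plans a record review to separate spontaneous from medically indicated delivery, for births before weeks 32 and 34 only.

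**The concern.** About three weeks of planned pessary use, from 34 0/7 to 36 6/7, have no clear between-arm efficacy comparison. A birth at 35 weeks is preterm by the protocol's own definition. Yet it appears only as an adverse event of special interest and in newborn tables that the SAP calls descriptive.

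Two things are at stake. First, a treatment that moves births from 33 to 35 weeks gives the same efficacy result as one that moves them to term. An exploratory trial of preterm birth prevention would want to tell these apart. Second, the gap is harder to close afterwards. Unless the 5.8 review is extended, spontaneous birth before 37 weeks cannot be derived on the same basis as the primary endpoint.

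**Working it through.** **1. The plan's own figure.** Protocol 9.1 claims at least 80% power with 90 women per group for a difference of 40% or more (two-sided 0.05, uncorrected chi-square). It gives no control rate and does not say whether 40% is relative or absolute, so the figure cannot be reproduced uniquely. Read as a relative reduction, 90 per arm gives 80% only at a control rate of about 51% (51% v 30.6%). The documents give no expected rate for enrolled women at 34 or at 37 weeks, so the rates in step 3 are assumptions.

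**2. What share of preterm births falls at 34 weeks or later?** Share = 1 − P(before 34)/P(before 37).

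- General population (Protocol 2): preterm birth is described as "affecting approximately 7% to 10% of births", and births by week 34 as 1.8% (England) or 1.3% (Chile). 1 − 1.8/7 = 74%; 1 − 1.3/10 = 87%. These rates combine spontaneous and iatrogenic births.
- Cervix ≤15 mm (Protocol 2): delivery before 32 weeks is 80.8% when found before week 20 and 48.1% when found at 20–24 weeks. P(before 34) is at least P(before 32), and P(before 37) is at most 100%. The share is therefore at most 1 − 0.808 = 19% or 1 − 0.481 = 52%.
- Higher-risk women with cervix <25 mm (Protocol 2): birth before 35 weeks is 70% or 40%, depending on when the short cervix is found. At most 30% or 60% of preterm births can then fall at 35–36 weeks.

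The trial enrols women with a cervix of 10–25 mm and women with a relevant obstetric history and any length from 10 mm. The share for that mixture cannot be derived.

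**3. Effect of the horizon on power.** Assumed control rates: 15% before 34 weeks (13.5 expected events in 90 women) and 30% before 37 (27 events). With p̄ the mean of the two rates:

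power = Φ{ [|p1 − p2|√n − 1.96√(2p̄(1 − p̄))] / √[p1(1 − p1) + p2(1 − p2)] }, n = 90.

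| Comparison, 40% relative reduction | Rates | Term in braces | Power |
|---|---|---|---|
| Before 34 weeks | 15% v 9% | (0.569 − 0.901)/0.458 = −0.72 | 23% |
| Before 37, late births respond equally | 30% v 18% | (1.138 − 1.184)/0.598 = −0.08 | 47% |
| Before 37, late births unaffected | 30% v 24% | (0.569 − 1.231)/0.626 = −1.06 | 15% |

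In the last row, the control rate falls only by the 6 points gained before 34 weeks. With a 30% reduction the three figures are 15% (15% v 10.5%), 28% (30% v 21%) and 10% (30% v 25.5%).

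The direction does not depend on the 15%/30% choice. Across control rates before 34 weeks of 10–30% and late shares of 30–60%, with a 40% reduction, power before 34 weeks is 17–47%. Before 37 weeks it is 22–99% if late births respond equally and 9–41% if they do not. In every combination tried, equal response raises power and no response lowers it.

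**4. Quartiles under truncation.** If the SAP's log-rank analysis stops at 34 0/7, a quartile is estimable only if the estimated curve shows that fraction delivered by then. At the assumed 15%, not even the 25th percentile is reached. Running to 36 6/7 helps only partly: 30% on capsules reaches the 25th percentile, but 18% or 24% on a pessary does not.

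**The case against.** The strongest reply is that the cut-off simply follows from the endpoint. The objective and primary outcome are spontaneous birth before 32 and 34 weeks. Protocol 2 gives a reason for the early focus: the burden falls mainly on neonates born before 32 weeks. The 37-week definition comes from safety reporting, and the SAP calls the Kaplan-Meier analysis exploratory. All of this stands, and nothing in the primary comparison needs to change on this account.

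Four stronger readings are tempting, and the documents do not support them:

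- *The analysis drops women at 34 0/7.* It does not. A woman undelivered at 34 0/7 contributes all her time at risk and counts as event-free in the curve and in the proportions. Only her later outcome goes unused.
- *Most preterm births in the trial are lost.* Only general-population rates support this. The cited figures for cervix ≤15 mm found before week 20 rule it out in that subgroup, and the enrolled mixture is undetermined.
- *The cut-off costs power.* This holds only if the effect extends to late births; otherwise the 37-week comparison is diluted. A supportive outcome would not raise the power of the primary comparison in any case.
- *The SAP's log-rank test certainly stops at 34 0/7.* That is the natural reading beside the 34-week rule, but the log-rank and quartile sentences set no limit.

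Nor is observation to 36 6/7 guaranteed. Women may be withdrawn after expulsion without timely repositioning or for low adherence (Protocol 5.5, 5.6), and the pessary may be removed on request or for an adverse event (5.7). What remains is a gap in supportive analysis and an unstated horizon.

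**Conclusion.** The point holds as a low-cost improvement and not as an error in the primary analysis. Treatment and planned follow-up run to 36 6/7, yet no efficacy comparison clearly counts a spontaneous birth between 34 0/7 and 36 6/7 as an event. The plan therefore cannot tell births delayed to 35 weeks from births delayed to term.

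The number of births affected is unknown for this population. The effect on power could go either way: 23% at 34 weeks against 47% or about 15% at 37 weeks. Those figures rest on assumed control rates of 15% and 30%, 90 women per arm and a 40% relative reduction. The case for the extra comparison rests on what it would show, since even a diluted 37-week result would indicate where the effect stops. The horizon of the SAP's log-rank test and quartiles needs stating whichever was intended.

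**What to change.** Keep the 32- and 34-week primary proportions and Kaplan-Meier readings. Then:

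1. In Protocol 9 and SAP 10, add a Kaplan-Meier and log-rank comparison run to 36 6/7, labelled supportive.
2. Add spontaneous birth before 37 0/7 by arm, with risk difference and 95% CI, also labelled supportive.
3. In SAP 10, state the horizon of the log-rank test and of the gestational-age percentiles and mean, and say how a quartile that is not reached will be reported.
4. In Protocol 5.8, extend the spontaneous-or-indicated review to all births before 37 0/7. This matters because Protocol 2 puts iatrogenic births at one third of those by week 34.

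The cost is protocol and SAP wording plus some additional record review for births that must already be reported within 24 hours. No new visit or participant is needed. The downside is one more secondary comparison, which may be diluted if the effect is confined to early births.

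Separately, the SAP defines its primary window as after 32 but before 34 weeks, while the protocol says before 32 and 34. The two should be reconciled when this text is revised.

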### 9.1. Sample Size

The calculation of the sample size is based on the power to detect differences in the proportion of spontaneous delivery before 32 and 34 weeks of gestation between the cerclage pessary formulations with respect to the control group (vaginal capsules containing 200 mg progesterone). Collecting data from at least 90 women in each group will provide a power of at least 80% to detect differences at a rate of 40% or more using a two-tailed test with  $\alpha=0.05$  for a non-corrected Chi square.

We estimate that up to 10% of enrolled women may not complete the study, so it is planned to enroll at least 99 pregnant women per group to reach at least 198 treated with the cerclage pessaries, and 99 treated with soft progesterone capsules as control group (i.e., 99 per vaginal formulation).

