The sample size calculation is based on the power to detect differences in the proportion of spontaneous birth between 32 and 34 weeks of gestation, between the formulations of cerclage pessaries with respect to the control group (vaginal progesterone 200 mg capsules). Data collected of at least 90 women in each group will provide at least 80% of the power to detect differences with a rate of 40% or more, using a test of Chi-square of two tails with $\alpha = 0.05$ without correction.

We estimate that up to 10% of the enrolled women may not complete the study, so it must be planned to enroll at least 99 pregnant women in each group to reach at least 198 treated subjects with cerclage pessary and 99 subjects treated with soft capsules of progesterone as a control group (i.e. 99 per each vaginal formulation).

RANDOMIZATION

The randomization will be generated by an independent statistician. The program will be linked in sequential numbers with the code of randomized treatment. A qualified staff member of ANDROMACO laboratory will keep randomization codification, until the database is clean and ready for analysis. The treatment will be dispensed according to the randomization code, the women with unique pregnancy enrolled, will be randomized to receive one of the vaginal formulations of the study.

For the next volunteer, the site will have the next randomization number available. Each woman will receive only the formulation corresponding to the randomization number. The Investigator will record on the log the randomization number and the printed code on each formulation container. Each sites coordinator will assign the randomization code to the volunteers.

Subjects will be randomized to the following three study groups:

- Control Group (A): Intravaginal capsule of micronized progesterone 200 mg on a daily basis.
- Pessary Group (B): Pessary with 6.3 g of sustained release progesterone for a period of around 4 to 5 months.
- Pessary Group (C): Pessary with 7.7 g of sustained release progesterone for a period of around 4 to 5 months.

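### Enrolment of 99 per group adds 10% to 90 instead of dividing by 0.90; at the plan's maximum loss it leaves about 89 completers per group, one short of the stated 90

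*Protocol*

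**What the plan says.** Protocol 9.1 rests its power statement on completers: "Collecting data from at least 90 women in each group will provide a power of at least 80" per cent. It then sets the allowance for loss as a share of those enrolled, "We estimate that up to 10% of enrolled women may not complete the study", and draws the enrolment figure from it: "so it is planned to enroll at least 99 pregnant women per group". The sample size paragraph of SAP section 3 says the same: "it must be planned to enroll at least 99 pregnant women in each group".

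The opening text of Protocol 9 shows how the allowance was calculated. It first writes that "270 pregnant participants at risk of preterm birth will be enrolled, screened, and randomized to the 3 groups of treatment previously described". The next sentence says that this number "refers to the number of patients who effectively are enrolled and successfully complete the study", and the one after it that "an enrollment of at least 10% over that number (27 patients or more) should be considered". Protocol 4.1 and SAP section 3 plan to recruit 270 plus 10%, and then describe that population as three groups of 90.

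**The concern.** The percentage is applied to the wrong base. If up to 10% of enrolled women are lost, the number enrolled must be large enough that 90% of it is still 90. Adding 10% to the 90 completers gives a slightly smaller number, so at its own maximum loss the plan falls just below the count on which its power statement depends.

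The completer count matters here because SAP section 6 makes the per-protocol set (women who completed the required visits, or continued until the pregnancy ended) the main efficacy population. Protocol 5.7 adds that women whose pessary is removed on request or for an unresponsive adverse event are not replaced.

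Separately, the text does not keep the number randomised and the number completing apart. The first sentence of Protocol 9 attaches randomisation to 270, and Protocol 4.1 and SAP section 3 divide a population of 270 plus 10% into groups of 90, although 297/3 = 99.

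**Working it through.** **Inputs**
- Women needed with data: 90 per group, 270 in total (Protocol 9.1 and 9).
- Loss: up to d = 0.10 of those enrolled (Protocol 9.1).
- Minimum enrolment: 99 per group (Protocol 9.1, SAP section 3); 27 or more above 270 (Protocol 9).
- Test: two-sided, alpha 0.05, uncorrected chi-square (Protocol 9.1).

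**Reproducing the plan's figure.** n x (1 + d):
- 90 x 1.10 = 99 per group
- 270 x 1.10 = 297 in total

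Both match the documents exactly, so this is the rule that was used.

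**The rule that fits the stated loss.** n / (1 - d):
- 90 / 0.90 = 100 per group
- 270 / 0.90 = 300 in total

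The difference is 1 woman per group and 3 overall.

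**What 99 leaves at 10% loss**
- 99 x 0.90 = 89.1 per group
- 297 x 0.90 = 267.3 in total

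**Loss that 99 can absorb.** 1 - 90/99 = 0.0909, or 9.1%. In whole women, 9 losses leave 90 and 10 losses leave 89.

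**Effect on power.** The documents give no control rate and do not say whether the 40% is absolute or relative, so the rates below are assumptions that serve only to judge size. For an uncorrected chi-square with n per group, power is approximately

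Phi{ [ |p1 - p2| x sqrt(n) - 1.96 x sqrt(2 x pbar x (1 - pbar)) ] / sqrt(p1(1 - p1) + p2(1 - p2)) }, with pbar = (p1 + p2)/2.

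For 40% against 20%, pbar = 0.30:
- n = 90: (0.20 x 9.487 - 1.270)/0.632 = 0.99, power 83.9%
- n = 89: (0.20 x 9.434 - 1.270)/0.632 = 0.97, power 83.5%

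| Assumed rates | n = 90 | n = 89 | Difference (points) |
|---|---|---|---|
| 60% vs 36% | 90.3% | 90.0% | 0.3 |
| 40% vs 20% | 83.9% | 83.5% | 0.4 |
| 50% vs 30% | 78.7% | 78.2% | 0.5 |
| 40% vs 24% | 63.5% | 63.1% | 0.5 |
| 20% vs 12% | 30.9% | 30.6% | 0.3 |

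The level of power depends heavily on the assumed rates. The loss from having 89 instead of 90 does not: it is about half a point or less throughout.

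**The case against.** The strongest reply is that the plan states bounds. Loss is capped at 10%, while 99 and the extra 27 are minimums. On expected numbers, 99 keeps 90 at any loss up to 9.1%, so the shortfall appears only when loss lies between 9.1% and 10% and enrolment stops at its floor. This stands, and it limits the point to the upper end of the plan's own range. It does not remove it, because a minimum enrolment should hold at the maximum loss that it is meant to cover.

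A second reply is that not completing is different from having no outcome. Protocol 5.5 to 5.7 keep withdrawn women in the analysis, and Protocol 5.8 takes the pregnancy outcome from hospital records or the treating physician. Some of the 10% would therefore still contribute data to an intention-to-treat analysis. This stands in part: it does not help the per-protocol analysis that SAP section 6 puts first.

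Two stronger readings are tempting and should not be drawn:
- **That only 270 will be randomised, so that the completers fall well below 90 per group.** The first sentence of Protocol 9, read alone, suggests this. The next two sentences define 270 as women completing and add at least 27. The Synopsis (270 with useful information for analysis), Protocol 4.1 (270 plus 10%), Protocol 9.1 and SAP section 3 (99 per group) all agree with that definition. The wording is loose, but the intended numbers are clear.
- **That the slip can be measured by the chance of an arm of 99 ending with fewer than 90.** An arm of 100, which is right on average, also has a substantial chance of ending below 90. Such a probability mostly reflects chance variation around a target set at the mean, and little of it is due to the choice of 99 over 100.

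**Conclusion.** The point holds as a small arithmetic slip. At the 10% ceiling, the minimum enrolment yields about 89 women per group (267 in total) against a stated requirement of 90 (270). The correct minimum is 100 per group (300).

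This rests on two conditions: loss above 9.1%, and enrolment no higher than the stated floor. The power consequence is negligible and can be given only on assumed rates. The absence of a control rate is a separate and larger question, and correcting 99 to 100 does not answer it. The double use of 270 is a matter of wording and leaves no open design question.

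**What to change.** In Protocol 9.1 and the sample size paragraph of SAP section 3, do one of the following:
- **Keep 99.** State that 99 per group (297) gives about 89 completers per group (267) at 10% loss, or that 99 covers a loss of up to 9% (99 x 0.91 = 90.1). This costs wording only, and the stated size becomes slightly less favourable. Quoting power for 89 would first need a stated control rate.
- **Write 100 per group (300).** This costs three more women. The dependent figures change with it: 198 and 99 treated become 200 and 100, and the 27 extra in Protocol 9 becomes 30.

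As a wording clean-up, revise the first sentence of Protocol 9 and the recruitment text in Protocol 4.1 and SAP section 3. In all three places 270 (90 per group) should be the number completing, and 297 (99 per group), or 300 (100 per group) under the second option, the number randomised.
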